5.4.2 STUDY ARM #2

5.4.2.a Out-Patient Day #1

- Participants will be admitted to the hospital research ward at about 7 A.M after overnight abstinence from e-cigarettes starting at 10 PM and 48 hours

- At the time of admission to the hospital ward, expired CO will be measured. Those with expired CO of 5 ppm or over will not receive the abstinence bonus. The participant will be given the option to delay study procedures until CO levels decrease or to be sent home without pay.
- Participants will be in a hospital-approved smoking room with negative pressure and a fan ventilating to the outside.
- At about 8 AM, an intravenous catheter will be placed in the forearm for blood sampling.

Standardized E-Cigarette Vaping Session

- At 9 AM, the participant will vape the study e-cigarette at the assigned power in a standardized protocol: one 4-second puff every 30 seconds for a total of 10 puffs.
- We are standardizing puff duration to minimize within- and between-subject variations in vaping topography.
- After each puff, participants will exhale into a gas trap to determine amount of nicotine exhaled.
- E-cigarettes will be weighed before and after use to determine the amount of nicotine inhaled.
- After this standardized session, the participant will abstain from using e-cigarettes for a 4-hour period.

4-hr Abstinence

- Heart rate will be measured before and at 5, 10, 15, 20, 25, and 30 minutes after product use.
- Withdrawal, craving and reward will be assessed before and immediately after the standardized session and at 2 and 4 hours after.
- Blood nicotine levels will be measured before and then at 2, 5, 15, 30, 45, 60, 90, 120, 180 and 240 minutes after completing product use.
- At the end of the 4-hour abstinence period, participants will be allowed 90 minutes of ad libitum access to the e-cigarette at the same assigned power level as during the standardized session.

90 minute *ad libitum* session

- Blood samples will be collected before and every 15 minutes from the beginning of the session.
- Withdrawal, craving, and reward will be assessed before and immediately after the session ends.
- Vaping topography (puff number, puff duration, and inter-puff interval) will be measured via digital video recordings that allow frame-by-frame analysis
- Participant will be free to go at the end of the ad-lib session, around 3:30

5.4.2.b Out-Patient Day #2

- Participants will be admitted to the hospital research ward at about 7 A.M after overnight abstinence from e-cigarettes starting at 10 PM and 48 hours abstinence from smoking tobacco cigarettes
- At the time of admission to the hospital ward, expired CO will be measured. Those with expired CO of 5 ppm or over will not receive the abstinence bonus. Study procedures will continue.
- Participants will wear an ambulatory blood pressure and heart rate recorder to assess circadian blood pressure, heart rate pattern, and heart rate variability (8 AM-8 PM).
- Participants will be free to vape the assigned product as they would like from 8 AM to 8 PM.
 - The time of each puff will be recorded by the participant using a mobile app (Nomie2) or paper log if app is unavailable.
- The e-cigarette will be weighed before and at the end of the day to determine the amount of e-liquid consumed, including if re-filled.
- Questionnaires to assess reward and craving and other nicotine withdrawal symptoms will be completed 4 times (8 AM, 12 noon, 4 PM and 8 PM).
- 12-Hour urine will be collected for assessment of various toxicant biomarkers and effects biomarkers.
- Blood will be sampled every four hours from 8 AM to 8 PM.
 - Nicotine will be measured in all blood samples and cardiovascular effects biomarkers will be measured in the 8 AM (pre-vaping) and 12 PM blood samples.
- Participants will be free to go home after the final blood draw and questionnaire at ~8 PM.

5.4.3 STUDY ARM #3

5.4.3.a Out-Patient Day #1

- Participants will be admitted to the hospital research ward at about 7 A.M. after overnight abstinence from e-cigarettes starting at 10 PM and 48 hours abstinence from smoking tobacco cigarettes.
- At the time of admission to the hospital ward, expired CO will be measured. Those with expired CO of 5 ppm or over will not receive the abstinence bonus. The participant will be given the option to delay study procedures until CO levels decrease or to be sent home without pay.
- Participants will be in a hospital-approved smoking room with negative pressure and a fan ventilating to the outside.
- At about 8 AM, an intravenous catheter will be placed in the forearm for blood sampling and light breakfast will be served.

Standardized E-Cigarette Vaping Session

- At 9 AM, the participant will vape the study e-cigarette at the assigned power in a standardized protocol: one 4-second puff every 30 seconds for a total of 10 puffs.
- We are standardizing puff duration to minimize within- and between-subject variations in vaping topography.
- After each puff, participants will exhale into a gas trap to determine amount of nicotine exhaled.
- E-cigarettes will be weighed before and after use to determine the amount of nicotine inhaled.
- After this standardized session, the participant will abstain from using e-cigarettes for a 4-hour period.

4-hr Abstinence

- Heart rate will be measured before and at 5, 10, 15, 20, 25, and 30 minutes after product use.
- Withdrawal, craving and reward will be assessed before and immediately after the standardized session and at 2 and 4 hours after.
 - Blood nicotine levels will be measured before and then at 2, 5, 15, 30, 45, 60, 90, 120, 180 and 240 minutes after completing product use
- At the end of the 4-hour abstinence period, participants will be allowed 90 minutes of ad libitum access to the e-cigarette at the same assigned power level as during the standardized session.

90-minute ad libitum session

- Blood samples will be collected before and every 15 minutes from the beginning of the session.
- Withdrawal, craving, and reward will be assessed before and immediately after the session ends.
- Vaping topography (puff number, puff duration, and inter-puff interval) will be measured via digital video recordings that allow frame-by-frame analysis
- Participant will be free to go at the end of the ad-lib session, around 3:30 pm.

5.4.3.b Out-Patient Day #2

- Participants will be admitted to the hospital research ward at about 7 A.M after overnight abstinence from e-cigarettes starting at 10 PM and 48 hours abstinence from smoking tobacco cigarettes
- At the time of admission to the hospital ward, expired CO will be measured. Those with expired CO of 5 ppm or over will not receive the abstinence bonus. Study procedures will continue.
- Participants will wear an ambulatory blood pressure and heart rate recorder to assess circadian blood pressure, heart rate pattern, and heart

- Participants will be free to vape the assigned product as they would like from 8 AM to 8 PM.
 - The time of each puff will be recorded by the participant using a mobile app (Nomie2) or paper log if app is unavailable.
- The e-cigarette will be weighed before and at the end of the day to determine the amount of e-liquid consumed, including if re-filled.
- Questionnaires to assess reward and craving and other nicotine withdrawal symptoms will be completed 4 times (8 AM, 12 noon, 4 PM and 8 PM).
- 12-Hour urine will be collected for assessment of various toxicant biomarkers and effects biomarkers.
- Blood will be sampled every four hours from 8 AM to 8 PM.
 - Nicotine will be measured in all blood samples and cardiovascular effects biomarkers will be measured in the 8 AM (pre-vaping) and 12 PM blood samples.
- Participants will be free to go home after the final blood draw and questionnaire at ~8 PM.

5.4.4 PARTICIPANT SCHEDULE

Study Arm #1: Power level 10, 15, or 20 watts (computer randomized, single-blinded)	
Hospital Day 1	Hospital Day 2

• Standardized Session• 4-hr abstinence and blood draws• Followed by 90 min Free use session w/ video monitoring	
• Free use• 12-hr CV monitoring• Circadian blood draws• 12-hr urine collection
Study Arm #2: 1 of the other 2 remaining power levels (computer randomized, single-blinded)	
Hospital Day 1	Hospital Day 2

• Standardized Session• 4-hr abstinence and blood draws• Followed by 90 min Free use session w/ video monitoring	
• Free use• 12-hr CV monitoring• Circadian blood draws• 12-hr urine collection
Study Arm #3: Remaining power level (computer randomized, single-blinded)	
Hospital Day 1	Hospital Day 2

• Standardized Session• 4-hr abstinence and blood draws• Followed by 90 min Free use session w/ video monitoring	
• Free use• 12-hr CV monitoring• Circadian blood draws• 12-hr urine collection

5.5 PARTICIPANT COMPENSATION

Participants will be compensated according to Table 2:

Table 2

Screening Visit	Abstinence ARM 1	Study Arm #1	Abstinence ARM 2	Study Arm #2	Abstinence ARM 3	Study Arm #3	Completion Bonus
\$30 (check)	\$40 (Day 1) + \$40 (Day 2) (include in check)	\$420 (check)	\$40 (Day 1) + \$40 (Day 2) (include in check)	\$420 (check)	\$40 (Day 1) + \$40 (Day 2) (include in check)	\$420 (check)	\$360 (in final check)
Total Compensation: \$1,890							

*Compensation for the screening visit will be contingent upon a negative toxicology drug screen (THC is okay) and a cotinine of ≥ 30 ng/ml.

6 ADVERSE EVENTS AND PROTOCOL DEVIATIONS

6.1 SAFETY MONITORING

During the inpatient stay, participants will be monitored by the CRC and the nursing staff who will directly contact the Study Physician in case of any subsequent adverse events. If the participants experience adverse effects, the Study Physician will evaluate this with them and decide if they should be withdrawn from this study.

6.2 REPORTING ADVERSE EVENTS

Reporting of serious adverse events will follow the current requirements of the UCSF Human Research Protection Program's Institutional Review Board (IRB), with the concurrent reporting to the Nurse Manager at the CRC. Specifically, the following will be reported within five (5) working days of the Principal Investigator's (PI) awareness, in writing:

- All serious adverse events associated with the study procedures and/or
- Any incidents or problems involving the conduct of the study or patient participation, including problems with the recruitment and/or consent process. The PI will provide a discussion of such events to the IRB on an annual basis during study renewal.
- Any incidents or questionable adverse events are discussed at the weekly staff meetings with the PI.

The standard adverse event grading scale will be used to report any potential adverse events from phlebotomy, study drug, or other study procedures:

- **Grade 1 - Mild AE:** did not require treatment
- **Grade 2 - Moderate AE:** resolved with treatment
- **Grade 3 - Severe AE:** resulted in inability to carry on normal activities and required profession medical attention
- **Grade 4 - Life-threatening or disabling AE**
- **Grade 5 - Fatal AE**

The supervising Study Physician will be notified of all Grades 2 through 5 AEs. Additionally, the PI will be notified of all grades 4 and 5 AEs. Grades 3 through 5 AEs will be reported to the CCRC and the CHR. Grades 4 and 5 will be reported within 24 hours. Grade 3 will be reported within 20 days. Grade 2 will be included in the yearly progress report. Grade 1 will not be reported.

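### Does Section 6.2 leave a serious Grade 3 event without an assured start to its 5-working-day reporting limit?

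*Protocol*

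**What the plan says.** Section 6.2 of the Protocol opens with serious events. They follow the IRB's current requirements, and "the following will be reported within five (5) working days" of the PI's awareness, in writing. The first item on that list is "All serious adverse events associated with the study procedures". The list also covers incidents or problems in the conduct of the study, and ends with "Any incidents or questionable adverse events are discussed at the weekly staff meetings with the PI".

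The section then gives a five-grade severity scale for events arising from study procedures. Grade 3 is an event that "resulted in inability to carry on normal activities and required profession medical attention"; Grade 4 is life-threatening or disabling, and Grade 5 is fatal. On notification, "The supervising Study Physician will be notified of all Grades 2 through 5 AEs", and additionally "the PI will be notified of all grades 4 and 5 AEs". Reports for Grades 3 to 5 go to the CCRC and the CHR, with these limits: "Grades 4 and 5 will be reported within 24 hours. Grade 3 will be reported within 20 days".

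Section 6.1 gives the first step on the ward: the CRC and nursing staff "directly contact the Study Physician in case of any subsequent adverse events", and the Study Physician evaluates the event and decides whether the participant should be withdrawn.

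**The concern.** The 5-working-day limit runs from the PI's awareness, so it does not start until the PI is told. Of the three grades with a limit in hours or days (3, 4 and 5), Grade 3 is the only one for which the PI is not named. The prescribed route for a Grade 3 event, in both 6.1 and the grade list, ends at the Study Physician, who is a separate role (Sections 8.1 and 8.3). The 20-day rule has no exception for serious events.

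Staff who worked from the grade list alone could therefore give a serious Grade 3 event 20 days, while the shorter limit never started. What would be at stake is late oversight reporting of a serious event.

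**Working it through.** **The rules side by side (Section 6.2)**

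| | Serious-event rule | Grade rule, Grade 3 |
|---|---|---|
| Turns on | Seriousness, any grade | Severity grade |
| Limit | 5 working days | 20 days (calendar or working not stated) |
| Starts at | PI awareness | Not stated |
| Recipient | IRB requirements govern | CCRC and CHR (not expanded) |

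The rules use different axes. A serious Grade 3 event meets both, and a report made within 5 working days of prompt PI awareness satisfies both. The serious-event rule is written for all such events, so the grade list needs no exception for it to apply. There is no contradiction.

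**How late could the PI learn before the 5-working-day limit overran the 20 days?**

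The Protocol gives no figure to reproduce. Assumptions: the 20 days run from the event, and there are no public holidays. Let *a* be the calendar day of PI awareness (event = day 0) and *L* the calendar length of 5 working days counted from day *a*. *L* is 7 from a weekday, 6 from a Saturday and 5 from a Sunday. The condition is *a* + *L* ≤ *D*, where *D* is the calendar day on which the 20-day limit ends.

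- *20 calendar days, D = 20.* Weekday awareness: *a* ≤ 20 − 7 = 13. Saturday: *a* ≤ 20 − 6 = 14. Sunday: *a* ≤ 20 − 5 = 15. Over the seven possible event weekdays, the latest acceptable awareness day is 13 to 15.
- *20 working days.* *D* = 28 for a weekday event, 27 for a Saturday, 26 for a Sunday. For Monday to Thursday events, *a* ≤ 28 − 7 = 21. For a Friday event, day 23 is a Sunday and 23 + 5 = 28, so *a* ≤ 23. For a Saturday event, day 22 is a Sunday and 22 + 5 = 27, so *a* ≤ 22. For a Sunday event, day 21 is a Sunday and 21 + 5 = 26, so *a* ≤ 21. The range is 21 to 23.

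**The weekly meeting**

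The next meeting is at most 7 days after the event. With awareness on day 7, a weekday, the limit ends on day 7 + 7 = 14. That is 6 days before day 20, and 12 to 14 days before the end of a 20-working-day limit (26 − 14 to 28 − 14). The shorter limit overruns only if the event is missed at the meeting and the PI does not otherwise learn of it for about two weeks or more.

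**Who is in the affected group**

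Life-threatening, disabling and fatal events are already Grade 4 or 5, with 24-hour reporting and PI notice. What remains is events that are serious on some other ground and graded 3. Section 6.2 does not define serious, so this overlap is inferred; the Protocol does not show what would fall in it.

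**The case for a change.** The strongest case for a change is that a limit starting at PI awareness binds no one until the PI is told, and no sentence requires that for a serious Grade 3 event. The weekly meeting is worded for incidents and questionable adverse events, which does not expressly cover every serious event. The duties listed for the Study Physician and the CRC (Sections 8.3 and 8.5) do not mention passing events to the PI. By contrast, Section 6.3 has the PI review and sign even deviations that carry no risk. The repair would be two or three sentences at almost no cost.

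As a reading of the text, this stands: an explicit notification sentence is absent. It does not stand as a defect in the plan. An event that stops normal activities and needs medical attention is an incident on any ordinary reading, and so is meeting business. The PI has oversight of implementation (Section 8.1), the trial has one site (Section 2.1) and 21 or 24 participants (Section 2.4.2), and each admission set-up includes an adverse event form (Section 5.2.1.f). The IRB requirements to which 6.2 defers may also settle how the PI is informed; they are not at hand.

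The obvious repair also carries a risk. The 20-day report goes to the CCRC and the CHR, and the Protocol does not show whether these are the same recipients as under the serious-event rule. Confining the 20 days to non-serious Grade 3 events could leave the CCRC and CHR report of a serious Grade 3 event with no stated limit.

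**Conclusion.** No change is called for. Section 6.2 omits an internal cross-reference that its staff would fill sensibly; it does not contain conflicting limits. For the lapse to occur, a serious event would have to be graded 3, be known to the Study Physician and ward staff, and still not reach the PI at the weekly meeting. Even then the Study Physician evaluates the event and a report is made within the Grade 3 limit. Only the date of an oversight report could move; no endpoint, analysis or conclusion depends on it.

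This rests on three assumptions: that the weekly meeting is held as described, that a serious Grade 3 event would be treated as an incident there, and that the 20 days run from the event. Whether they are calendar or working days does not alter the result. If Section 6 is revised for other reasons, a line linking the two schemes and naming the recipient of each report would help readers, with the existing limits left in place. It is optional.

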6.3 PROTOCOL DEVIATIONS & VIOLATIONS

Protocol deviations are defined as an event that deviates from the defined study protocol, but does not pose any risk to the participant or harm to the quality of the study data. For example, a follow-up call may be conducted outside of the stipulated window, or a section of questions on a questionnaire may be missed due to a mistake in branching. Deviations will be recorded on a protocol deviation sheet and reviewed and signed by the PI.

Protocol violations are events that deviate from the defined study protocol, but put the participant at risk and/or cause harm to the study data. Protocol violations will be recorded on a protocol violation sheet, reviewed and signed by the PI and reported to the IRB

7 DATA COLLECTION AND MANAGEMENT

7.1 DATA COLLECTION FORMS

All of the following measures will be collected.

Screening Process:

- UCSF Tobacco Research Center Online Screen

In-Person Screening Visit:

- TCORS-Study 1 Screening Packet

Inpatient Study Visits:

- Minnesota Nicotine Withdrawal Scale (MNWS)
- Questionnaire on Smoking Urges-Brief (QSU-brief)
- Modified Cigarette Evaluation Questionnaire (mCES), further modified for e-cigarettes
- Appeal and Sensory Effects Questionnaire
- Perceptions of Risk Questionnaire

8 DUTIES AND RESPONSIBILITIES OF STAFF

8.1 PRINCIPAL INVESTIGATOR

The Principal Investigator is responsible for study design and oversight of implementation, data analysis, and manuscript preparation.

8.2 CO-PRINCIPAL INVESTIGATORS

The Co-Principal Investigators are responsible for study design and oversight of implementation, data analysis, and manuscript preparation, with the assistance of the Principal Investigator.

8.3 STUDY PHYSICIAN

The Study Physician is responsible for medical study chart review and eligibility determination, medical history and physical examination at SFGH admissions, and other medically related expertise.

8.4 CLINICAL RESEARCH SUPERVISOR

The Clinical Research Supervisor is responsible for overall functioning of study coordination with IRB protocols; monitoring of study budget and coordination with departmental administrative personnel; supervision of research associates; management of clinic facilities.

8.5 CLINICAL RESEARCH COORDINATOR

The CRC will oversee study logistics including consenting and screening participants, conducting study visit procedures, coordinating inpatient admissions and procedures with nursing staff at the research ward, coordinating specimen testing with laboratory, overseeing participant reimbursement, maintaining study charts and data entry.
